[figure not shown]

Vfend Special Investigation

- Investigation For Treatment of Invasive Fungal Infections in Pediatric Patients -

NON-INTERVENTIONAL (NI) STUDY PROTOCOL

STUDY INFORMATION

Title	Special Investigation of Vfend - Investigation for Treatment of Invasive Fungal Infections in Pediatric Patients -
Protocol ID	A1501100
Protocol version identifier	Ver. 1.0
Date of last version of protocol	N/A
Active substance	Voriconazole
Medicinal product	Vfend 200 mg for Intravenous Use Vfend Tablets 50 mg Vfend Tablets 200 mg Vfend Dry Syrup 2800 mg
Research question and objectives	
This study is intended to assess the following items, etc. for the safety and effectiveness of Vfend 200 mg for Intravenous Use, Vfend Tablets 50 mg, Vfend Tablets 200 mg, and Vfend Dry Syrup 2800 mg (hereinafter referred to as Product) in daily clinical practice for invasive fungal infections in children and review the necessity for further special investigation and post-marketing clinical study.
 
- Unknown adverse reactions- Occurrence of adverse reactions under actual clinical settings- Factors considered to affect the safety and effectiveness of this product
Author	PPD Post Marketing Study Strategy and Management PMS Planning and Operation Group 1

TABLE OF CONTENTS

1. LIST OF ABBREVIATIONS.....	4
2. RESPONSIBLE PARTIES.....	5
3. AMENDMENTS AND UPDATES.....	6
4. MILESTONES.....	6
5. RATIONALE AND BACKGROUND.....	6
6. RESEARCH QUESTION AND OBJECTIVES	7
6.1. Safety Specifications	7
7. RESEARCH METHODS	7
7.1. Study design	7
7.2. Setting.....	7
7.2.1. Inclusion criteria	7
7.2.2. Exclusion criteria.....	10
7.2.3. Sites for this study	10
7.2.4. Planned investigation period.....	10
7.2.5. Study procedure.....	10
7.2.6. Observation period.....	10
7.3. Variables.....	10
7.3.1. Background.....	11
7.3.2. Targeted drug use record	12
7.3.3. Concomitant therapy.....	12
7.3.4. Tests.....	12
7.3.5. Final diagnosis (name of infection)	13
7.3.6. Completion (discontinuation) record.....	13
7.3.7. Effectiveness evaluation	14
7.3.8. Adverse events.....	14
7.3.9. Major investigation items	15
7.4. Data sources	16
7.5. Study size	16
7.5.1. Planned sample size.....	16
7.5.2. Rationale for sample size.....	16

7.6. Data management.....	16
7.6.1. Data collection method.....	16
7.6.2. Patient registration.....	16
7.6.3. Reminders concerning completion, revision, and submission of case report form	17
7.7. Data analysis	17
7.8. Quality control.....	18

1. LIST OF ABBREVIATIONS

Acronym	Title
AE	adverse event
Al-P	Alkaline phosphatase
ALT	Alanine aminotransferase
AST	Aspartate aminotransferase
BUN	Blood urea nitrogen
CRP	C-reactive protein
EDP	exposure during pregnancy
GGT	Gamma-glutamyltransferase
IEC	Independent Ethics Committee
IRB	institutional review board
NIS	Non interventional study
SRSD	Single Reference Safety Document

3. AMENDMENTS AND UPDATES

N/A

4. MILESTONES

Milestone	Planned date
Start of data collection	Jun 2015
End of data collection	Jun 2018
Final study report	To be decided

5. RATIONALE AND BACKGROUND

Vfend (nonproprietary name: voriconazole) is a new triazole therapeutic agent for invasive fungal infections developed by Pfizer UK Central Laboratory which has a similar structure as fluconazole.

Vfend selectively acts on fungal cells and demonstrates its antimycotic activity by inhibiting cytochrome P450-dependent 14 α -demethylase in the ergosterol biosynthesis which is a component of fungal cell membranes.

Vfend 200 mg for Intravenous Use, Vfend Tablets 50 mg, and Vfend Tablets 200 mg were approved as drugs indicated for invasive aspergillosis, pulmonary aspergilloma, chronic necrotic pulmonary aspergillosis, candidaemia, esophageal candidiasis*, candidal peritonitis, bronchopulmonary candidiasis, cryptococcal meningitis, pulmonary cryptococcosis, fusariosis, and scedosporiosis on 11 April 2005.

Furthermore, since the options for antimycotic agents which can be used for pediatric patients are limited in Japan, "the Review Committee on Unapproved or Off-Labeled Drugs with High Medical Need" held in April 2010 evaluated that the pediatric indication of voriconazole had high medical need and requested the development of voriconazole for pediatric use. The pharmacokinetic study of voriconazole in pediatric patients was conducted in Japan and the pediatric indication of voriconazole was approved on 26 September 2014. In so doing, since the dosage and administration in children need to be adjusted per weight and the use of tablets in younger children is expected to be difficult, the approval of oral dry syrup was also obtained as a new dosage form.

Special Investigation of Vfend - Investigation for Treatment of Invasive Fungal Infections in Pediatric Patients - (hereinafter referred to as "this study") will be conducted to collect information on occurrence of adverse reactions by Vfend 200 mg for Intravenous Use, Vfend Tablets 50 mg, Vfend Tablets 200 mg, and Vfend Dry Syrup 2800 mg by type of diseases, etc., quality, effectiveness and safety under the actual clinical settings in daily clinical practice for children. The information collected from this study shall be used to provide proper use information and prepare documents for the application of re-examination.

This Study shall be conducted in strict compliance with the "Ordinance concerning Standards for Conducting Post-Marketing Study and Studies on Pharmaceutical products" (MHLW Ordinance No. 171 dated December 20, 2004)

Data obtained from the patients registered in this study will be reported to the MHLW pursuant to the Pharmaceutical and Medical Device Act; pertinent to which, data may be publicly posted in MHLW's

"Pharmaceuticals and Medical Devices Safety Information" and "Pharmaceuticals and Medical Devices Information Website (<http://www.info.pmda.go.jp>)" as a listing of patients, which will present the names of drugs, adverse reactions, sex, age (increment of 10 years), and other relevant information. Furthermore, data collected may also be disclosed if the MHLW is required to disclose such information in accordance with the "Act on Access to Information Held by Administrative Organs" (Law No. 42 dated May 14, 1999) provided that in no event will the names of physicians, medical institutions, and other personal information be subject to such disclosure, nor will it be posted or disclosed in any form or shape.

* Only for tablets and dry syrup

6. RESEARCH QUESTION AND OBJECTIVES

This study is intended to assess the following items, etc. for the safety and effectiveness of Vfend 200 mg for Intravenous Use, Vfend Tablets 50 mg, Vfend Tablets 200 mg, and Vfend Dry Syrup 2800 mg (hereinafter referred to as this product) in daily clinical practice for invasive fungal infections in children and review the necessity for further special investigation and post-marketing clinical study.

- Unknown adverse reactions
- Occurrence of adverse reactions under actual clinical settings
- Factors considered to affect the safety and effectiveness of this product

6.1. Safety Specifications

[Important identified risks] Hepatic toxicity, QT prolongation, ventricular tachycardia, ventricular fibrillation, arrhythmia, complete atrioventricular block, visual events, phototoxicity, peripheral neuropathy such as Guillain-Barre syndrome, renal disorder, hematologic disorder, interstitial pneumonia, cardiac failure, consciousness disorder

[Important potential risks] None

[Important missing information] Safety of pediatric use

7. RESEARCH METHODS

7.1. Study design

This study is a prospective multicenter cohort study conducted in patients receiving this product; for which, case report forms will be recorded based on data presented in medical records obtained in daily clinical practice.

7.2. Setting

Patients under the age of 15 years with severe or intractable fungal infection at the initiation of treatment with this product are subject to this study.

7.2.1. Inclusion criteria

1. Patients under the age of 15 years at the initiation of treatment with this product
2. Patients with invasive fungal infections

The indications, and dosage and administration of this product are as follows. The latest package insert should be referred to when administering this product.

[INDICATIONS]

Severe mycosis as follows:

- Invasive aspergillosis, Pulmonary aspergilloma, Chronic necrotic pulmonary aspergillosis.
- Candidemia, Esophageal candidiasis*, Candidal peritonitis, Bronchopulmonary candidiasis.
- Cryptococcal meningitis, Pulmonary cryptococcosis.
- Fusariosis.
- Scedosporiosis. * Only for tablets and dry syrup

[DOSAGE AND ADMINISTRATION]

<for Intravenous Use>

Adult	Voriconazole is administered by intravenous drip infusion at the dose of 6 mg/kg twice daily on day 1 and 3 mg/kg or 4 mg/kg twice daily from day 2 onward.
Children (Aged 2 to <12 and ≥12 whose body weight is less than 50 kg)	9 mg/kg as voriconazole twice daily on day 1 and 8 mg/kg twice daily from day 2 should be given intravenously. Dose may be increased if poorly responded by 1 mg/kg at a time, and dose in intolerant patients should be reduced by 1 mg/kg at a time.
Children (Aged ≥12 whose body weight is 50 kg or more)	6 mg/kg as voriconazole twice daily on day 1 and 4 mg/kg twice daily from day 2 should be given intravenously.

<Tablet>

Adult (body weight ≥40 kg)	A recommended oral dose of voriconazole is 300 mg/dose twice daily between meals on day 1, and 150 or 200 mg/dose twice daily between meals on day 2 and thereafter. Dose may be increased depending on condition of patients or if poorly responded; provided that a total daily dosage should not exceed 400 mg/dose twice daily on day 1 and 300 mg/dose twice daily on day 2 and thereafter.
----------------------------	--

Adult (body weight <40 kg)	A recommended oral dose of voriconazole is 150 mg/dose twice daily between meals on day 1, and 100 mg/dose twice daily between meals on day 2 and thereafter. Dose may be increased from day 2 onward depending on condition of patients or if poorly responded; provided that a total daily dosage should not exceed 150 mg/dose twice daily.
Children (Aged 2 to <12 and ≥12 whose body weight is less than 50 kg)	After the administration of Voriconazole injection, a recommended maintenance oral dose of voriconazole following injection therapy is 9 mg/kg/dose twice daily between meals. Dose may be increased by 1 mg/kg at a time if poorly responded, and dose in intolerant patients should be reduced by 1 mg/kg at a time (unless the dosage was at its maximum 350 mg, in which case, dose should be reduced by 50 mg at a time). A total daily dosage should not exceed 350 mg/dose twice daily.
Children (Aged ≥12 whose body weight is 50 kg or more)	After the administration of Voriconazole injection, a recommended maintenance oral dose of voriconazole following injection therapy is 200 mg/dose twice daily between meals; which may be increased up to 300 mg/dose twice daily if poorly responded.

<Dry Syrup>

Adult (body weight ≥40 kg)	A recommended oral dose of voriconazole is 300 mg/dose twice daily between meals on day 1, and 150 or 200 mg/dose twice daily between meals on day 2 and thereafter. Dose may be increased depending on condition of patients or if poorly responded; provided that a total daily dosage should not exceed 400 mg/dose twice daily on day 1 and 300 mg/dose twice daily on day 2 and thereafter.
Adult (body weight <40 kg)	A recommended oral dose of voriconazole is 150 mg/dose twice daily between meals on day 1, and 100 mg/dose twice daily between meals on day 2 and thereafter. Dose may be increased from day 2 onward depending on condition of patients or if poorly responded; provided that a total daily dosage should not exceed 150 mg/dose twice daily.
Children (Aged 2 to <12 and ≥12 whose body weight is less than 50 kg)	After the administration of Voriconazole injection, a recommended maintenance oral dose of voriconazole following injection therapy is 9 mg/kg/dose twice daily between meals. Dose may be increased by 1 mg/kg at a time if poorly responded, and dose in intolerant patients should be reduced by 1 mg/kg at a time (unless the dosage was at its maximum 350 mg, in which case, dose should be reduced by 50 mg at a time). A total daily dosage should not exceed 350 mg/dose twice daily.

Children (Aged ≥ 12 whose body weight is 50 kg or more)	After the administration of Voriconazole injection, a recommended maintenance oral dose of voriconazole following injection therapy is 200 mg/dose twice daily between meals; which may be increased up to 300 mg/dose twice daily if poorly responded.
--	---

7.2.2. Exclusion criteria

Patients who correspond to the following must not be registered to this study.

- Patients who have been registered to this study before

7.2.3. Sites for this study

Sites with presence of doctors specialized in the target therapeutic area primarily in the following departments, at which, the product can be prescribed:

Departments of pediatrics, pediatric hematology, etc.

7.2.4. Planned investigation period

Investigation period: June 2015 to June 2018

Registration period: June 2015 to March 2018

(Registration will be discontinued even before the end of the registration period if the target number of patients is reached.)

7.2.5. Study procedure

7.2.5.1. Study methods

This study will be conducted with a central registration system.

7.2.6. Observation period

The observation period shall start on the day the treatment with this product begins and end on the day the treatment is completed; provided that it will be cut off at Week 16 of treatment (Day 112 counting from Day 1 as the day the treatment begins) if the treatment prolongs.

7.3. Variables

This study will be conducted in accordance with the following assessment schedule.

Table 1. Schedule of observation

Variables		Timing	Baseline	Observation period	Termination of observation period
Background	ID number		•		
	Sex		•		
	Age at the time when the treatment of the targeted drug is initiated		•		
	Height/body weight		•		
	Hospitalization status (inpatient/outpatient)		•		
	Objective of treatment		•		
	Disease history		•		
	Presence/absence of fever unresponsive to antibacterial agents		•		
	Prior medications for infection for which this product is prescribed		•		
Presence/absence of pregnancy				•	
Targeted drug use record				•	
Therapeutic drugs and concomitant medications for careful administration/contraindication for infection				•	
Laboratory tests				•	
Final diagnosis (name of infection)				•	
Effectiveness evaluation					•
Completion (discontinuation) record					•
Confirmation of presence/absence of adverse events which correspond to major investigation items (presence/absence of occurrence of hepatic toxicity/visual events)				•	
Adverse events				•	

• : Data items

7.3.1. Background

Input the information at the initiation of this product.

- (1) ID number
- (2) Sex
- (3) Age (at the time when the targeted drug is initiated)
- (4) Height
- (5) Body weight
- (6) Hospitalization status (inpatient/outpatient)
- (7) Objective of treatment (infection for which this product is prescribed)
 - Treatment of mycosis/others
 - Severity
- (8) Disease history (information on diseases other than target diseases)
 - Presence/absence and severity of hepatic function disorder, renal impairment

- Name of disease or syndrome, as well as history or pre-existing disease
- (9) Presence/absence of fever unresponsive to antibacterial agents
- (10) Prior medications for infection for which this product is prescribed (name of antifungal agent administered to the target disease from 2 weeks before treatment of this product until the day before the start date of treatment, route of administration, reason for discontinuation)

7.3.1.1. Presence/absence of pregnancy

Input the presence/absence of pregnancy from the start date of treatment until the completion of observation period (date of delivery (abortion) or expected date of delivery if the patient is pregnant).

7.3.2. Targeted drug use record

The following will be recorded for the treatment status of this product.

- (1) Dosage form
- (2) Dose
- (3) Body weight used for calculation of adjustment of this product
- (4) Frequency of dose
- (5) Treatment period

7.3.3. Concomitant therapy

7.3.3.1. Therapeutic drugs and concomitant medications for precautions/contraindication for infection for which this product is prescribed

The following information will be recorded for therapeutic drugs and concomitant medications for careful administration/contraindication for infection for which this product is prescribed from the initiation of treatment with this product to the completion date of observation period.

- (1) Drug name (product name)
- (2) Route of administration
- (2) Treatment period

7.3.4. Tests

7.3.4.1. Mycological test

Input assumed causative fungi used for diagnosis of invasive fungal infections (input for each collected material/assumed causative fungi).

- (1) Testing material
- (2) Testing method
- (3) Assumed causative fungi (name of fungi, date of sample collection, fungal volume)
- (4) Result of susceptibility test

7.3.4.2. Serological test

Input the results of serological test used for diagnosis of invasive fungal infections.

- (1) Date of collection of sample used for diagnosis
- (2) Testing method (β -D-glucan, D-arabinitol, candida antigen, candida mannan antigen, candida antibody, cryptococcus neoformans antigen, cryptococcus antibody, aspergillus antigen, aspergillus antibody etc.)
- (3) Cut-off value
- (4) Test results

7.3.4.3. Imaging test

Input the results of the imaging test which was conducted by the initiation of treatment with this product and used for diagnosis of invasive fungal infections (input for each test site).

- (1) Test site
- (2) Test date
- (3) Presence/absence of findings suspected of invasive fungal infections

7.3.4.4. Plasma voriconazole concentration

If the plasma concentration of voriconazole was measured, input the test results.

- (1) Date and time of blood collection
- (2) Date and time of treatment with this product immediately before blood collection
- (3) Plasma voriconazole concentration

7.3.4.5. Laboratory tests

Input the following test items and test items for adverse events.

[Observation items] White blood cell count, neutrophil count, platelet count, total bilirubin, AST, ALT, Al-P, GGT, CRP, BUN, serum creatinine

7.3.5. Final diagnosis (name of infection)

Diagnose the name of infection from clinical symptoms, results of mycological test, serological test, etc.

Follow the latest guideline for diagnosis and treatment of invasive fungal infections for determination of patients with definite diagnosis and suspected diagnosis.

7.3.6. Completion (discontinuation) record

If the observation is completed or discontinued before the end of the longest observation period (16 weeks), the reason should be recorded.

If an adverse event is selected for the reason, the information in details should be recorded in the adverse event column.

[Reason for completion]
- Cured (effective)

[Reason for discontinuation]
- Insufficient clinical effectiveness

- Adverse events
- No revisit
- Hospital transfer
- Other

7.3.7. Effectiveness evaluation

7.3.7.1. Clinical response

The clinical response of this product should be evaluated based on the clinical course excluding the mycological response at the end of the observation period.

If this product is used continuously for more than 16 weeks, the clinical response should be evaluated comprehensively at Week 16.

- Effective
- Not effective
- Indeterminate (In this case, the reason should be recorded.)

Reason in the case of indeterminate

- Because the diagnosis is not "invasive fungal infections" or "invasive fungal infections suspected"
- Other

7.3.7.2. Mycological response

The mycological response should be determined at the end of the observation period and the results should be recorded.

- Eradication: The causative fungi detected from the focus before treatment with this product has become negative
- Presumed eradication: In the case when the focus improved and the collection of test material became impossible
- Decreased: The causative fungi decreased
- No change: There is no change in causative fungi
- Increased: The causative fungi increased (including the case of microbial substitution)
- Indeterminate: In the cases when the follow-up was inadequate, the causative fungi were not detected, or the mycological test was "not conducted"

7.3.8. Adverse events

Confirm the status of adverse events from the initiation of treatment with this product to the completion of observation period, and record the following information. Upon discovery of an adverse event, the attending doctor should take appropriate actions, and promptly report to Pfizer Japan Inc. (hereinafter "Sponsor"), and if causal relation with this product cannot be ruled out, the doctor should follow up the event until the adverse event or its sequelae are resolved or stabilized at the level acceptable by the attending doctor and Sponsor.

Moreover, a study should be conducted on patients in whom a serious adverse reaction, or an adverse reaction not specified in the package insert occurred if it is determined necessary by Sponsor.

- (1) Presence/absence of adverse event
- (2) Name of adverse event
- (3) Date of occurrence
- (4) Action
- (5) Seriousness
- (6) Outcome
- (7) Causality

[If the adverse event is associated with abnormal change in laboratory values, i.e., laboratory tests, the following information should also be recorded.]

- (1) Laboratory parameter
- (2) Site reference value
- (3) Unit
- (4) Date of test
- (5) Results

7.3.9. Major investigation items

The following items will be major investigation items in this study.

- (1) Hepatic toxicity

For patients who developed events related to hepatic toxicity including abnormal hepatic function test values, assess the occurrence status and the differences in patient background, dose, etc. between patients who can continuously receive treatment with this product and patients who must discontinue treatment with this product.

- (2) Visual events

Set the presence or absence of visual events as an investigation item. Assess the occurrence status for patients who developed visual events and the differences in patient background, dose, etc. between patients who can continuously receive treatment with this product and patients who must discontinue treatment with this product.

7.3.9.1. Confirmation of presence/absence of adverse events that correspond to major investigation items

7.3.9.1.1. Presence/absence of hepatic toxicity

The presence/absence of hepatic toxicity including hepatitis, jaundice, hepatic failure, coma hepatic, ALT (GPT) increased, AST (GOT) increased, and γ -GTP increased should be recorded for target patients in this study. If aggravation or new occurrence of hepatic toxicity is observed, the information in details should be recorded in the adverse event column.

7.3.9.1.2. Presence/absence of occurrence of visual events

The presence/absence of aggravation or new occurrence of visual events including photophobia, vision blurred, and visual disturbance should be recorded for target patients in this study. If aggravation or new occurrence of visual event is observed, the information in details should be recorded in the adverse event column.

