7.5.2. Rationale for sample size

The target sample size was set out to 100 patients who developed hepatic toxicity or visual events which are major investigation items for whom differences between patients who can continuously receive this product and patients who must discontinue the treatment with this product can be evaluated.

In the reports of adverse reactions in the clinical study (study A1501096) conducted for Japanese children (from 2 years old to under 15 years old), there were 4 patients with hepatic toxicity including abnormal hepatic function test values (19.0%) and 9 patients with visual events (42.9%). If the number of patients to be collected is set out to be 100, the number of patients from whom these events can be detected at a probability of 95% or higher is estimated to be 13 patients and 35 patients respectively. The 100 patients is the number of patients from whom adverse reactions that occur at the frequency of 3% or higher can be detected in at least 1 patient at a probability of 95% or higher.

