5.4. Subgroups

Subgroup analyses of safety will be performed for the following patient background factors. Levels in parentheses are levels of subgroups, and underlined levels are the reference for calculation of risk ratio and risk difference.

- Hepatic dysfunction [absent, present]
- Renal dysfunction [absent, present]
- Age (children 1) [newborns (<1 month after birth), infants (≥ 1 month to <1 year), younger children (≥ 1 to <7 years), children (≥ 7 to <15 years)]
- Age (children 2) [<2 years, ≥ 2 years]
- Diagnostic name (name of infection) [invasive aspergillosis, pulmonary aspergilloma, chronic necrotic pulmonary aspergillosis, candidemia, esophageal candidiasis, candida peritonitis, bronchopulmonary candidiasis, cryptococcal meningitis, pulmonary cryptococcosis, fusariosis, scedosporiosis, other invasive fungal infections, others]
- Severity [mild, moderate, severe]
- Fever unresponsive to antibacterial agents [absent, present]
- Use of concomitant medications requiring precautions for coadministration [absent, present]
- Concomitant antifungal agents [absent, present]
- Prior medications (antifungal agents) [absent, present]
- Treatment period [<1 week, ≥ 1 to <2 weeks, ≥ 2 to <4 weeks, ≥ 4 to <8 weeks, ≥ 8 to <12 weeks, ≥ 12 to ≤ 16 weeks]
- Long-term treatment [≤ 12 weeks, >12 weeks]
- Dose on the first day (mg/kg) [<6, ≥ 6 to <7, ≥ 7 to <8, ≥ 8 to <9, ≥ 9 to <10, ≥ 10 , unknown]
- Mean maintenance dose (mg/kg) [<6, ≥ 6 to <7, ≥ 7 to <8, ≥ 8 to <9, ≥ 9 to <10, ≥ 10 , unknown]

Subgroup analyses of safety will be performed for the following:

- Pregnant and parturient women (pregnancy confirmed)
- Presence or absence of overdose^a

Patients who may meet contraindications in the package insert of Vfend (hereinafter referred to as contraindicated patients) will be extracted based on separately specified criteria, and subgroup analyses of safety will be performed.

Subgroup analyses of efficacy (clinical response) will be performed for the following patient background factors. Levels in parentheses are levels of subgroups, and underlined levels are the reference for calculation of risk ratio and risk difference.

- Hepatic dysfunction [absent, present]
- Renal dysfunction [absent, present]
- Age (children 1) [newborns (<1 month after birth), infants (≥ 1 month to <1 year), younger children (≥ 1 to <7 years), children (≥ 7 to <15 years)]
- Age (children 2) [<2 years, ≥ 2 years]

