The number and proportion of patients with major investigation items will be tabulated. The number and proportion of patients with major investigation items by intervention (change in treatment with Vfend) and outcome will be tabulated by SOC and PT.

The number and proportion of patients with adverse drug reactions considered as major investigation items will be calculated by intervention (change in treatment with Vfend) to assess whether treatment with Vfend was discontinued because of the onset of the adverse drug reaction after its onset.

The listing of patient background and concomitant medications will be prepared in patients with major investigation items with high incidence to evaluate factors common to patients with major investigation items.

- **Timing of onset of adverse drug reactions**

The number of patients with major investigation items and adverse drug reactions observed in $\geq 10\%$ of patients will be tabulated by SOC and PT by timing of initial onset [<1 week, ≥ 1 to <2 weeks, ≥ 2 to <4 weeks, ≥ 4 to <8 weeks, ≥ 8 to <12 weeks, ≥ 12 to ≤ 16 weeks].

For major investigation items and adverse drug reactions observed in $\geq 10\%$ of patients, time to event onset will be summarized in accordance with Section 8.1.4 with the initial onset of the adverse drug reaction considered as an event. Patients without adverse drug reactions will be censored after the observation period + follow-up period (28 days). Patients for whom the duration of the observation period + follow-up period exceeds 112 days will be censored at Day 112.

- **Relationship between concomitant medications and development of adverse drug reactions**

The number of patients with hepatic toxicity and visual events will be tabulated overall and by PT by presence or absence of actually used concomitant medications to evaluate the relationship of contraindicated concomitant medications and concomitant medications requiring precautions for coadministration with adverse drug reactions considered as major investigation items. However, medications started to be used after the day of the last onset of the event during the observation period + 28 days will be excluded from tabulation.

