8.2.3.4. Subgroup Analysis

The number and proportion of patients who experienced at least one adverse drug reaction will be tabulated for each factor specified in Section 5.4. To evaluate the relationship between patient background factors and the development of adverse drug reactions, the analysis specified in Section 8.1.3 will be performed. The same analysis will be performed for serious adverse drug reactions.

The listing of adverse drug reactions will be prepared for contraindicated patients. The number and proportion of patients with adverse drug reactions will be tabulated by SOC and PT as necessary.

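### Visual events are summarised over all ages with no guaranteed breakdown by age, so the rate may be diluted by children too young to report symptoms and is not like for like with the planning rate

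*Protocol*

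**What the plan says.** - **Eligibility.** Protocol 7.2.1 and 7.6.2.1 set an upper age limit (under 15 years) and no lower one. SAP 5.4 plans for the youngest patients: its first age factor begins with "newborns (<1 month after birth), infants", and its second splits at 2 years.
- **Recording.** For visual events, one of the two major investigation items, Protocol 7.3.9.1.2 states that "presence/absence of aggravation or new occurrence of visual events including photophobia, vision blurred, and visual disturbance should be recorded for target patients". If an event is seen, details go in the adverse event column. No level for patients who cannot be assessed and no age-appropriate assessment is described. Protocol 7.4 takes the data from medical records.
- **Analysis of the item.** SAP 8.2.3.1 says: "The number and proportion of patients with major investigation items will be tabulated". Further splits are by intervention, outcome, timing of onset and concomitant medication. A Kaplan-Meier summary is also planned, with event-free patients censored at the end of observation plus 28 days, or at Day 112. None of these is split by age.
- **Analysis by age.** SAP 8.2.3.4 says: "The number and proportion of patients who experienced at least one adverse drug reaction will be tabulated for each factor specified in Section 5.4". The same is done for serious reactions. SAP 8.2.3.5 adds a table by organ class and event term for any factor with a risk ratio of at least 2 or at most 0.5.
- **Planning rate.** Protocol 7.5.2 takes 42.9% (9 patients) from a study in children "from 2 years old to under 15 years old".

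**The concern.** The two major investigation items differ in how they come to light. Hepatic toxicity includes raised laboratory values, which can be found at any age. Photophobia, blurred vision and visual disturbance mostly need a child who can describe them. In chart-based collection, a symptom that nobody voices is likely to go unrecorded. Such a patient would still be in the denominator of the visual-event proportion and would be censored as event-free in the Kaplan-Meier summary.

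Protocol 6.1 lists safety of pediatric use as the missing information. Protocol section 15 ties further action to an increased frequency of reactions, or to problems compared with the period before approval. If part of the cohort cannot register the event, a rate below 42.9% could be read as better tolerability when some of the gap comes from detection. Such a comparison would err towards reassurance. Protocol 7.9 mentions missing chart data in general terms but not this mechanism.

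**Working it through.** **Inputs.** Planned size is 100 (Protocol 7.5.1). There were 9 patients with visual events, 42.9%, and 4 with hepatic toxicity, 19.0% (Protocol 7.5.2). Both percentages imply 21 patients: 9/21 = 0.4286 and 4/21 = 0.1905. Two quantities are not in the documents and are assumed: f, the share of the cohort unable to report a visual symptom, and s, the share of those children's events that carers or clinicians still notice.

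**Step 1: the plan's own figures.** Take the largest r with P(X ≥ r) ≥ 0.95 for a binomial count with n = 100.
- Visual, p = 9/21: r = 35, P = 0.955 (r = 36 gives 0.932).
- Hepatic, p = 4/21: r = 13, P = 0.958 (r = 14 gives 0.926).
- Reaction at 3%: 1 − 0.97^100 = 0.952.

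All three statements in Protocol 7.5.2 reproduce. The sample-size arithmetic is not in error.

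**Step 2: dilution.** Suppose the true rate is the same at all ages, there are no false positives, and undetected cases count as event-free. Then

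observed rate = p × (1 − f + f × s).

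With s = 0: 0.4286 × 0.90 = 0.386; × 0.80 = 0.343; × 0.70 = 0.300. With s = 0.5: 0.4286 × 0.95 = 0.407; × 0.90 = 0.386; × 0.85 = 0.364.

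| f (assumed) | Rate, s = 0 | Change, points | Rate, s = 0.5 | Count reached with ≥95% probability, s = 0 | P(at least 35), s = 0 |
|---|---|---|---|---|---|
| 0% | 42.9% | 0 | 42.9% | 35 | 95.5% |
| 10% | 38.6% | −4.3 | 40.7% | 31 | 79.8% |
| 20% | 34.3% | −8.6 | 38.6% | 27 | 47.8% |
| 30% | 30.0% | −12.9 | 36.4% | 23 | 16.3% |

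The relative loss in the rate is f × (1 − s). The 95% count has to be recomputed at each rate and does not simply scale: 35 × 0.80 = 28, against an exact 27.

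**Step 3: can the planned tables show it?**
- The age analysis in SAP 8.2.3.4 pools all reactions. Visual events missed in the youngest children can be masked there by reactions that do not depend on self-report.
- SAP 8.2.3.5 would show visual terms by age, but only if an age factor passes the risk-ratio threshold. The only risk ratios planned are those for any or any serious reaction.
- SAP 8.1.3 drops the risk ratio when the compared subgroups have 5 patients or fewer. A very small group under 2 years may therefore never reach the trigger. The same section keeps counts and proportions in that case.
- The background listing in SAP 8.2.3.1 covers patients who had the event and gives no denominators.

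**The case against.** A reader might infer that visual events are never broken down by age, that sites must enter 'absent' for a child who cannot report, and that the incidence is therefore biased downward. The documents do not support that much.

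- SAP 8.2.3.5 provides a conditional route to a table by age, and the listings will show the ages of cases. The amendment log gives small numbers as the reason for removing subgroup analyses of the major investigation items, so this was a reasoned choice.
- The case report form is not among the documents. Presence/absence wording does not prove two response levels: Protocol 7.3.1 uses it for hepatic and renal impairment, and SAP 8.2.2 tabulates those with an unknown level. SAP section 7 treats blank items as missing. Signs noticed by others can be recorded as adverse events.
- The share unable to report is not given. Labelled pediatric dosing in Protocol 7.2.1 starts at 2 years, so few younger children may be enrolled.
- The planning rate is imprecise. The exact 95% interval for 9/21 is 21.8% to 66.0%, and every diluted rate above lies inside it.
- No formal comparison with study A1501096 is planned. The stated use of the item is to compare patients who continue treatment with those who discontinue, among those who had the event.
- A cut at 2 years leaves some children who cannot describe their vision, and the earlier study's rate may share that limitation.

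Most of this stands, and it limits the claim to possible dilution of unknown size. It does not supply the missing presentation. No text removes a patient with an unknown entry from the denominator. The conditional table is not triggered by visual events themselves. Fewer detected cases would also shrink the group available for the comparison of continuers with discontinuers.

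**Conclusion.** The point holds in a limited form. The main visual-event rate and Kaplan-Meier summary pool all ages under 15 years for an item that depends largely on self-report, and no unconditional analysis separates the youngest children. The all-patient rate is therefore not like for like with the 42.9% from ages 2 to under 15 years. It is diluted to the extent that children who cannot describe vision count as event-free.

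Each 10% of the cohort in that position costs 4.3 points if none of their events is noticed, and half of that if half are noticed. This assumes the planning rate is the true rate at every age. The documents fix neither the share unable to report nor how sites enter such children, so the size, and whether it matters in practice, cannot be settled from them. The change is still worth making because it uses only data already collected.

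**What to change.** In SAP 8.2.3.1:

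1. Report the visual-event proportion with its exact 95% confidence interval, and the Kaplan-Meier summary, for patients aged 2 years and over beside the all-patient figures.
2. Show patients under 2 years separately as counts and proportions, which SAP 8.1.3 allows even in very small groups.
3. State with the table that detection of visual symptoms is limited in the youngest children, including some aged 2 years and over, and that the restricted figure matches the age range of study A1501096.

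If the case report form can still be changed, add a 'not assessable' level to the visual-event item and give the proportion among assessable patients as well. This is probably too late: data collection was planned to end in June 2018, and the current SAP is dated 20 September 2018.

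The cost is one or two extra table rows and a slightly smaller denominator for the age-restricted figure. Age is already collected, and the split at 2 years is already defined in SAP 5.4.
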